Blood samples will be collected in EDTA-blood collection tubes and centrifuged, then serum will be frozen at -80 degrees at UNC Project Malawi until transport to Houston, Texas. Stool samples will be frozen at -80 degrees until transport to Houston, Texas. Coded serum samples- without personal identifiers- will be sent to the laboratory of [name] at the National School of Tropical Medicine Baylor College of Medicine for determination of levels of immune activation and gut mucosal impairment (sCD14, sCD163, and I-FABP) and *Strongyloides stercoralis* IgG. Stool samples will be processed by stool microscopy in the local UNC Project Malawi laboratory, then the remaining sample will be transported to Houston, Texas to be processed by qPCR for detection of 10 different parasites and quantification of parasite burden at the Laboratory of Parasitology National School of Tropical Medicine Baylor College of Medicine. Urine samples will be brought to UNC Project Malawi for processing and evaluation by microscopy to look for *Schistosoma haematobium*.

The COVID-19 precautions followed by the study team are as follows: all subjects will complete a clinical questionnaire before entry into the clinic. Only those with low risk for current infection with SARS-CoV-2 will be approached for the study. All clinical team members will be wearing gloves and a surgical mask at the time of participant enrollment. All patients are required to wear a mask in the clinic and will be given gloves when they are given the stool sample collection kit.

After enrollment is completed, the serum and stool samples will be shipped to Houston, Texas. Stool samples will be processed by multi-parallel real-time quantitative PCR (qPCR) for detection of 9 different parasites and quantification of parasite burden. Parasites to be evaluated include *Ascaris lumbricoides*, *Ancylostoma duodenale*, *Necator americanus*, *Schistosoma mansoni*, *Strongyloides stercoralis*, *Taenia solium*, *Trichuris trichiura*, *Entamoeba histolytica*, and *Giardia lamblia*. Serum will be processed for *Strongyloides stercoralis* IgG, sCD14, sCD163, and I-FABP.

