We anticipate enrollment of 100 patients receiving care at the participating clinics during the recruitment period. With an estimated intestinal parasite prevalence of 30%, we predict 30 cases and 70 controls will be enrolled. This estimate is based on a study with similar patient population in the same region in 2007 which reported 17.3% of participants infected with helminth infections and 12.8% with pathogenic protozoal infections⁴. Our prevalence may be higher than this prior study given the increased sensitivity of our stool PCR test. Participants found to be positive at both the initial and follow up visit will be considered reinfected rather than treatment failure. These will be included in the analysis of prevalence, but the change in markers of immune activation will not be measured in this group since parasite clearance not established. Using Student's unpaired t-test to compare mean values of biomarkers between study groups, we will have 80% power to detect a difference of 0.434 x10⁶ pg/ml, 0.56 mg/l, and 598 pg/ml between groups for biomarkers sCD14, sCD163, and I-FABP, respectively with effect sizes within the range of prior studies^{9,14,59}. Using paired t-tests to compare pre- and post-treatment biomarker levels, we will have 80% power to detect post-treatment changes of 0.317 x10⁶/ml, 0.41 mg/l, and 435 pg/ml in sCD14, CD163, and I-FABP respectively⁶⁰. A sample size less than 100 increases the chance of a type II error where a true difference in markers of chronic inflammation does not reach clinical significance. A sample size of greater than 100 should not be necessary given the estimated findings in our patient population and the data presented by the studies cited above. A sample size of 100 should be easily attainable in a reasonable amount of time (4-8 weeks) without the unnecessary use of additional resources.

Clinical variables including age, sex, and most recent CD4 count will be recorded. Clinical predictors of parasitic infection (eg CD4%) will be determined using multivariable logistical regression. Univariable linear regression will be used to determine associations between markers of immune activation (continuous outcome variable) and predictors including the clinical variables above as well as presence of multiple parasitic infections.

Study visits:

- v0= Screening visit: includes explanation of study, inclusion/exclusion criteria, sign ICF
- v1= Baseline visit: complete CRF; collection of blood, stool, and urine samples

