- v2= Treatment visit: only for those participants positive for parasitic infection
- v3= Post-treatment/follow-up visit performed 8-12 weeks after administration of antiparasitic therapy to those participants found to be parasite-positive. Sample collection from controls (parasite-negative participants) will be done in a similar time window.

*screening and baseline visits can be done the same day

**Participants positive for parasitic infection will complete v0, v1, v2, v3. Participants negative for

parasitic infection will not have v2. Full participation in the study for a parasite negative participant includes completion of v0, v1, v3.

***Participants will be reimbursed for v1, v2, v3.

Ethical Considerations

In addition to the Malawi National Health Sciences Research Committee, we will submit for IRB approval from University of North Carolina School of Medicine, and the National School of Tropical Medicine at Baylor College of Medicine. Participation in the study will be voluntary. All study participants will be explained the study design and all questions answered before the participant provides written, informed consent.

Neither the investigator, nor any research team member will coerce or unduly influence nor specifically target vulnerable subjects to participate in the study. Research subjects will be informed that participation is voluntary and that they are free to withdraw from the study for any reason at any time. Subjects will be given time to ask questions, and if agreeable they will sign consent and then study procedures will be initiated. The investigator will keep the original consent form as part of the study records, and a copy will be provided to the subjects. A Chichewa translator will be present for the entirety of each interaction with each participant.

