The possibility of a breach in confidentiality will be minimized by limiting the number of people that will have access to the information, the use of coded data, and the stringent security measures that will be utilized. Only [name] and members of the research team will have access to the patient clinical data. The Participant Information Sheet with clinical information will only have the participant codes and deidentified clinical information. The informed consent forms and the "link-log form" with patient names and patient codes will be kept in a locked cabinet at UNC Project Malawi. Information entered into the electronic database will only include the participant identification number. The patient names will not be included in the electronic database. The database will not be saved on personal computers, rather will only be saved to a secure UNC server and will be password protected.

Work Plan

We plan to begin enrollment of participants starting January 2022. We estimate that 2-3 months will be sufficient to recruit 100 participants. After 100 participants are enrolled and samples collected, we will send samples to Houston, Texas. We expect it will take 1-2 months to process all of the samples in the laboratory of [name]. Follow up visits will take place 2-3 months after participants with parasitic infections were treated. Once follow up visits completed and samples obtained, the second shipment of samples will be sent to Houston, Texas. We expect another 1-2 months for the processing of samples in the laboratory of [name]. Once all samples are processed, laboratory analysis can be performed. A manuscript will be prepared and submitted for publication. An infectious diseases journal will be the target for publication of the manuscript. The NHSRC will be provided a copy of the manuscript. Additionally, we plan to present our findings at both a local and an international academic conference.

VI. References

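### The only planned test of biomarker change is a before-after t-test in treated cases, so any shift common to everyone counts as a treatment effect; the controls' change is never used

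*Combined protocol and SAP*

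**What the plan says.** The Aim 2 hypothesis (Objectives) has two parts: the markers are higher in co-infected than in parasite-negative participants, and they fall after anti-parasitic treatment.

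The sample size and analysis paragraphs under Subjects and Methods name three analyses that involve the markers:

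- A Student's "unpaired t-test to compare mean values of biomarkers between study groups". It concerns levels and names no visit.
- The test of change: "Using paired t-tests to compare pre- and post-treatment biomarker levels, we will have 80% power to detect post-treatment changes" of 0.317 x10⁶ (sCD14), 0.41 mg/l (sCD163) and 435 pg/ml (I-FABP). A pre- and post-treatment pair exists only for treated cases. Cases positive at both visits drop out: "the change in markers of immune activation will not be measured in this group since parasite clearance not established".
- A regression: "Univariable linear regression will be used to determine associations between markers of immune activation (continuous outcome variable) and predictors". The outcome is the marker itself; neither change nor visit is mentioned.

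The Study visits list adds, for v3: "Sample collection from controls (parasite-negative participants) will be done in a similar time window". No analysis is attached to those control samples.

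On handling, Subjects and Methods states: "After enrollment is completed, the serum and stool samples will be shipped to Houston, Texas". In the Work Plan, once follow-up is complete, "the second shipment of samples will be sent to Houston, Texas", and "We expect another 1-2 months for the processing of samples".

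**The concern.** A one-group before-after test estimates the treatment effect plus everything else that moved the marker between v1 and v3. Here that includes calendar time, storage time and possibly assay round. A common fall would look like benefit from deworming; a common rise could hide a real one.

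The plan makes such a shift plausible. Baseline and follow-up samples travel in separate shipments with separate processing periods, and nothing is said about assay runs or calibration. The interval between the two samples is also long and varies with enrollment order.

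The only related evidence is in the paragraph on follow-up timing: sCD14 and sCD163 did not change from week 8 to week 24 in a hepatitis C treatment study. That is another population, it omits I-FABP, and it does not address assay round.

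The planned control samples at v3 could remove an additive common shift, but the plan does not say they will be used for this.

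**Working it through.** **Inputs from the plan.** 30 predicted cases and 70 controls; 80% power; the three paired changes above (sCD14 read as x10⁶ pg/ml); unpaired detectable differences of 0.434 x10⁶ pg/ml, 0.56 mg/l and 598 pg/ml.

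**Assumed, because not stated.** Two-sided alpha 0.05, normal-theory t-tests and, in the base case, no losses. No SD is given, so the SDs of change are back-calculated.

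**1. The plan's own figure.** The 80% cannot be reproduced independently without alpha and SDs. The figures are coherent with each other: the paired/unpaired ratios are 0.317/0.434 = 0.730, 0.41/0.56 = 0.732 and 435/598 = 0.727. With noncentral t, a paired test on n = 30 has 80% power at a standardised change d = 0.5292. The implied SDs of change are:

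- sCD14: 0.317/0.5292 = 0.599 x10⁶ pg/ml
- sCD163: 0.41/0.5292 = 0.775 mg/l
- I-FABP: 435/0.5292 = 822 pg/ml

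**2. Paired test with no treatment effect and a common shift of s SDs.** The noncentrality is s√30 on 29 df.

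| Shift (SD of change) | sCD14 equivalent (x10⁶ pg/ml) | Paired test significant |
|---|---|---|
| 0.05 | 0.03 | 6% |
| 0.1 | 0.06 | 8% |
| 0.2 | 0.12 | 19% |
| 0.5 | 0.30 | 75% |

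**3. Case-versus-control comparison of change.** An additive common shift cancels. Simulated rejection at 30 versus 70, with no treatment effect and a 0.2 SD common shift:

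| Case SD / control SD | 0.67 | 0.8 | 1 | 1.25 | 1.5 |
|---|---|---|---|---|---|
| Welch | 5% | 5% | 5% | 5% | 5% |
| Student | 2% | 3% | 5% | 7% | 9% |

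Welch is therefore the safer choice with unequal group sizes.

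**4. Precision cost.** With equal SDs, the noncentrality is d/√(1/30 + 1/70) = d/0.2182 on 98 df, and 80% power needs d = 0.6174. The ratio to the paired test is 0.6174/0.5292 = 1.167. Detectable effects become 0.370 x10⁶ pg/ml, 0.478 mg/l and 507 pg/ml (Welch: 0.372, 0.481, 511). At the stated changes, power is 67% (Welch 66%). Keeping 80% there would need about 136 participants split 30:70.

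With unequal SDs and the case SD held at 0.599, the Welch detectable effect for sCD14 is 0.342 (8% above 0.317) if the case SD is 1.5 times the control SD, and 0.434 (37% above) if the control SD is 1.5 times the case SD.

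**5. Losses.** At an assumed 24 evaluable cases, the paired test itself falls to 70% power at the stated changes. The equal-SD comparison has 60% at 24 versus 70 and 57% at 24 versus 56. Compared with the paired test at 24 (d = 0.5972), the cost is 0.6697/0.5972 = 1.12 and 0.6921/0.5972 = 1.16.

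**6. Interval from v1 to v3 for a case found by qPCR**, ignoring shipping and contact time:

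- Shortest (last enrolled): 1 month of processing + 8 weeks ≈ 2.8 months.
- Longest (first enrolled): 3 months of recruitment + 2 months of processing + 12 weeks ≈ 7.8 months on the Work Plan's recruitment estimate.
- The sample size paragraph instead expects recruitment in 4 to 8 weeks, which puts the longest interval at about 5.7 to 6.6 months.

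**The case against.** **The plan does not rule the comparison out.** The unpaired test names no visit, controls are followed to v3, and participants found pregnant at follow-up are excluded from the marker comparison, which suggests that v3 values enter some comparison. This stands as far as intent goes. But the unpaired test is worded for mean values, its detectable differences are not those quoted for change, and the pregnancy rule names no contrast of change. Collecting samples is not specifying an analysis.

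**Separate assay rounds are inferred.** The Work Plan also says laboratory analysis can follow once all samples are processed, which could mean one pooled run. That is fair: the documents leave it open, although Subjects and Methods lists the markers with the first shipment. Pooling would not remove calendar-time change or unequal storage.

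**The 75% is nearly built in.** A 0.5 SD shift is 0.5/0.529 = 94% of the effect the test was sized to detect. Correct, and shifts of 0.05 to 0.1 SD do little harm (6% to 8%). The true drift is unknown, so the range matters and no single row should be read as a prediction.

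**The interval may be shorter.** The 4-to-8-week recruitment figure lowers the upper limit, and cases found by local microscopy may be treated sooner. Accepted; neither makes the interval negligible.

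**The remedy is not randomised and costs power.** Both are true. It does not undo the removal of cases positive at both visits, and the plan would still need a rule for controls who are positive at v3. None of this supplies the missing comparison.

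**Conclusion.** The concern holds. As written, the treatment half of Aim 2 rests on an uncontrolled before-after test, although control follow-up samples are already planned. Any v1-to-v3 shift shared by everyone would be read as a treatment effect. With no treatment effect, false significance ranges from about 6% to 75% for common shifts of 0.05 to 0.5 SD of change, against about 5% for a Welch comparison of change.

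These figures assume two-sided alpha 0.05, 30 complete pairs and normal-theory SDs back-calculated from the stated changes. The size of any real drift is unknown, and separate assay rounds are likely but not explicit. The plan's quoted power figures are not shown to be wrong; they belong to a test that cannot isolate treatment. The point should be settled before follow-up visits are scheduled and samples assayed, because a contrast chosen after results are seen would carry less weight.

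**What to change.** 1. Name the case-versus-control comparison of v1-to-v3 change as the main Aim 2 treatment analysis, by Welch test or a group-by-visit model that allows unequal variances. Keep the paired t-test as supportive.
2. Define the calendar anchor for control v3 visits. Controls have no treatment date, so their interval must be set to match the cases'.
3. Assay each participant's v1 and v3 samples in the same run where stored sample allows, and describe runs and calibration.
4. Restate alpha, SDs and detectable effects for this comparison after expected losses, including cases positive at both visits. State how controls positive at v3 are handled.
5. State the limits: the comparison removes only shifts common to both groups. Controls are uninfected, so regression to the mean or a proportional assay shift could remain, and the result is not a randomised treatment effect.

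**Cost.** No new participants or visits, provided a detectable effect about 17% larger is accepted at 30 versus 70 with equal SDs (8% to 37% larger with Welch over the SD ratios examined). Holding 80% power at the stated changes would instead take about 136 participants. The rest is the work of scheduling control visits and of holding or re-assaying stored v1 samples.

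### Baseline and follow-up biomarkers are assayed in two laboratory rounds months apart, so assay batch coincides with visit in the paired before-after test

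*Combined protocol and SAP*

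**What the plan says.** Two places describe the handling of samples.

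- **Methodology, Subjects and Methods.** "After enrollment is completed, the serum and stool samples will be shipped to Houston, Texas". The same paragraph lists the assays on that serum: "Serum will be processed for *Strongyloides stercoralis* IgG, sCD14, sCD163, and I-FABP".
- **Work Plan, first round.** "After 100 participants are enrolled and samples collected, we will send samples to Houston, Texas". Then: "We expect it will take 1-2 months to process all of the samples in the laboratory".
- **Work Plan, second round.** "Follow up visits will take place 2-3 months after participants with parasitic infections were treated". After that: "Once follow up visits completed and samples obtained, the second shipment of samples will be sent to Houston, Texas". A separate laboratory period follows: "We expect another 1-2 months for the processing of samples".

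The sample-size paragraph of Subjects and Methods names paired t-tests as the comparison of marker levels before and after treatment. It states 80% power for changes of 0.317 x10⁶ (sCD14), 0.41 mg/l (sCD163) and 435 pg/ml (I-FABP). The Study visits list has parasite-negative controls resampled at v3 in a similar time window.

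The document does not mention a retained baseline aliquot, a joint run, bridging or control samples, a common kit lot, or a batch term in the analysis.

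**The concern.** Half of Aim 2 is the hypothesis that the three markers fall after antiparasitic treatment. The paired t-test in treated participants is the only analysis named for it. If all v1 samples are measured in round one and all v3 samples in round two, a difference in calibration or reagent lot moves every pair in the same direction. The test would read that movement as treatment effect. It could report a fall that did not happen or hide one that did.

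The error is systematic, so a larger sample does not dilute it. A larger sample makes the test more likely to declare the shift significant.

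**Working it through.** **The plan's own figures.** The detectable changes cannot be reproduced directly, because the document gives no SD, no significance level and no within-person correlation. I took a two-sided 5% level and the 30 cases that the plan predicts, and solved backwards.

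- Paired t-test, n = 30, 80% power (noncentral t): standardised detectable change d = 0.529.
- Implied SD of change = stated change / 0.529:
  - sCD14: 0.317 / 0.529 = 0.60 x10⁶
  - sCD163: 0.41 / 0.529 = 0.77 mg/l
  - I-FABP: 435 / 0.529 = 822 pg/ml

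**What the test estimates.** Let τ be the true mean change and b the difference between rounds. The mean observed change in cases is τ + b, and the paired t-test tests τ + b = 0. Nothing in the data from cases alone separates the two terms.

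**False positives when τ = 0.** Write b as a fraction f of the detectable change. The noncentrality is f × 0.529 × √30 = f × 2.899, on 29 degrees of freedom.

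| f | Shift: sCD14 (x10⁶) / sCD163 (mg/l) / I-FABP (pg/ml) | Rejection rate, 30 pairs |
|---|---|---|
| 0 | 0 / 0 / 0 | 5.0% |
| 0.10 | 0.032 / 0.041 / 44 | 5.9% |
| 0.25 | 0.079 / 0.10 / 109 | 10.8% |
| 0.50 | 0.159 / 0.205 / 218 | 28.9% |
| 0.75 | 0.238 / 0.31 / 326 | 55.6% |
| 1.00 | 0.317 / 0.41 / 435 | 80.0% |

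The last row equals the planned power by construction. Simulation with 20,000 replicates agrees: 5.1%, 29.0% and 80.0% at f = 0, 0.5 and 1.

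**Masking.** If the true change equals the detectable change and the shift runs the other way, the net effect is (1 − f) of it. Power falls from 80% to 55.6% at f = 0.25 and to 28.9% at f = 0.50.

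**Sample size.** With 60 pairs and the same absolute shifts, the false-positive rates at f = 0.25 and 0.50 rise to 17% and 52%.

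**Using the controls.** If change in cases is compared with change in controls, a common additive shift cancels: (τ + b) − b = τ. With 30 cases and 70 controls, simulated type I error stays between 4.8% and 5.1% for f = 0, 0.5 and 1. The standardised detectable difference is 0.617 in place of 0.529, a factor of 1.17. If both groups have the same SD of change, the detectable changes become about 0.370 x10⁶, 0.478 mg/l and 507 pg/ml. Power at the plan's stated changes falls from 80% to about 67%.

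**The case against.** The strongest reply is that the data as collected are not beyond rescue. Controls give v3 samples in a similar time window and, as written, pass through the same two rounds. Their change would estimate a common shift, and the calculation above shows that this works. That stands, and it limits the claim: batch and treatment are fully confounded in the within-case paired test, not in everything the design could estimate. But the plan names no such analysis, and relying on it costs power that joint assay would keep.

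A second reply is that two shipments need not mean two marker runs, since the document is silent on plates, lots and retained aliquots. A joint run is not ruled out. However, Subjects and Methods lists the three markers among the assays on the serum shipped after enrolment, and the Work Plan has all first-round samples processed before follow-up. Two rounds is the plain reading. If a joint run is intended, one sentence would say so.

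A third reply is that the rejection rates say nothing about how large a real shift would be. That is correct. At 10% of the detectable change the harm is slight, and nothing in the document shows which row of the table applies.

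**Conclusion.** The concern holds for the planned before-after comparison. On the plain reading of Subjects and Methods and the Work Plan, assay round coincides exactly with visit, and the paired t-test has no protection against a shift between rounds. The false-positive rate runs from 5.9% at a shift of 10% of the detectable change to 80% at a shift equal to it.

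These figures assume 30 pairs, a two-sided 5% level, an additive shift common to all samples in a round, and SDs implied by the plan's own detectable changes. The plan leaves out of the change analysis participants who are positive at both visits. Under its 30% prevalence there would then be fewer than 30 pairs and less than 80% power.

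The baseline comparison of infected and uninfected participants is unaffected, because both groups are in the first round. The plan should be changed, because the remedy is cheap and is lost if baseline serum is used up in the first round without a reserve.

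**What to change.** 1. Ship v1 stool, and the blood needed for *Strongyloides* IgG, as planned. Keep a separate v1 aliquot per participant at -80 for the three markers.
2. After the second shipment, assay sCD14, sCD163 and I-FABP for v1 and v3 of the same participant on the same plate and reagent lot. Mix infected and control participants on each plate, and blind the laboratory to visit and group. Samples are already coded, but the plan does not say that the code conceals either.
3. State this batching in the Work Plan.
4. As a supporting analysis, compare change in cases with change in controls, on the log scale if batch effects are likely to be multiplicative. If joint assay proves impossible, this becomes the fallback, with the loss of power shown above.

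The cost is one extra aliquot per participant and later baseline marker results. Treatment follows from parasite detection, so no treatment decision waits on them. The number of marker assays is the same. The downside is that v1 aliquots are stored some months longer than v3 aliquots. Control samples share this difference, so the supporting analysis in step 4 also covers it.
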